**16.0 Potential Benefits to Subjects\***

16.1-16.2. We do not expect a direct benefit to participants. However, participants may learn new information about clinical trials and research.

As feasible, participants will be referred to research nurses and/or research teams if they are identified as possibly eligible for a study/trial and interested in being contacted.

**17.0 Data Management\* and Confidentiality**

17.1. We will conduct various statistical tests on the data to determine whether participants experienced changes in knowledge, attitudes, behavioral intentions, and behavior as a results of any of the study arms, and changes will be look at across groups.

17.2. To ensure confidentiality of data, we will have several safeguards in place:

- Training: All research team members with access to study data will be trained on all procedures related to data management under this protocol.
- Access restrictions: Access to electronic research materials/data will be limited to those on the research team. This will include only granting electronic access to Qualtrics and One Drive/Sharepoint to study team members, these sites/applications also require passwords to access. All laptops/computers being used will also be encrypted and password-protected. Access to physical research materials/data will also be limited by being stored in locked filing cabinets at DHH.
- Unique identifiers: We will assign a unique identifier to the study information using the numbers provided by NCI/CRCHD/its contractor. We will link the pre-, post-, and follow-up enrollment data using the unique identifiers. Contact information requested from participants for purposes of follow-up to be referred and gift card distribution will be managed and stored separately from the study data but will be obtained in

**PROTOCOL TITLE:** Education about Health and Cancer Study

the same survey; after data are downloaded from Qualtrics, participant contact information will be stored and managed separately, with use of unique identifiers. The participant contact information and key to link data back to identifiers will be stored separately from the research data.

- Experimental Arm 1 participants asked to participate in a follow-up survey (post survey) will receive a shortened version of their unique identifier as part of the request for their participation in the follow-up/post survey and asked to manually enter their number into Qualtrics to facilitate our linking of their research records. See Experimental Arm 1 Qualtrics survey.

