## PROTOCOL TITLE: Education about Health and Cancer Study

		

-Removing control group

-Updating experimental arm 1 procedures

-Minor other edits

 
Updated survey for experimental arm 2 (and former control group)
 

-Removing control group intervention and 'dummy' questions from the control group

-Updating contact information throughout

-Providing clarifying instructional language

-Adding two qualitative questions about the intervention

 
Providing electronic surveys (pre and post) for experimental arm 1
 
Updated consent for experimental arm 2 (and former control group):
 

-Updating contact information

 
Updated consent for experimental arm :
 

-Updating study details

-Updating compensation

-Updating contact information

	
10	7/13/2021	

-Updating contact information for research team (instructional language in surveys, consent)

-Updating participant instructions related to timeline for compensation

-Updating study procedures for identifying bot/fake survey responses

	Y
11	9/10/2021	

-Updating PI

-Updating documents (including consents) to reflect updated PI

-Updating materials related to trials/studies we will refer to, as they also are experiencing changes in their PIs

	Y
12	3/3/2022	

-Updating recruitment plans/verbiage for Experimental Arm 2

-Clarifying team members mentioned in protocol (though they've previously been updated in eIRB system)

	N
13	05/02/2022	

Name change from Norris Cotton Cancer Center to Dartmouth Cancer Center

-Addition of new employees; removing previous employees

-Updating info for new Best Practice Alert for provider access to connect patients with clinical trials education

-Updating/clarifying listserve & Front Porch Forum information for advertising purposes

	
14	02/15/2023	

-Addition new employee; remove former employee

-Addition After Visit Summary (AVS) for Epic to BPA

-Study Population Arm 2 updated to include listserves and flyers in addition to social media

	

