## 1.0 Study Summary

Study Title	Education about Health and Cancer Study
Study Design	Interventional/Cohort Study Pre-/Post-/Follow-up (via surveys and research records)
Primary Objective	Aim 1: Implement and evaluate educational activities to improve knowledge of, attitudes and behavioral intentions toward, and participation in clinical trials and cancer research studies among rural residents living in NH and VT (Rural = RUCC 7-9 counties).
Secondary Objective(s)	
Aim 1a: Implement electronic portal access to educate regarding what clinical trials and cancer research are and evaluate the effect on knowledge of, attitudes and behavioral intentions toward, and actual enrollment into clinical trials and cancer research studies.
 
Aim 1b: Implement online education regarding what clinical trials and cancer research are and evaluate the effect on knowledge of, attitudes and behavioral intentions toward, and actual enrollment into clinical trials and cancer research studies.
 
Aim 1c: Compare the impact of education about clinical trials with the impact of an innovative outreach modality using social media and web-based technology for educating the public about clinical trials; provider portal Epic (EDH) for patients.

Research Intervention(s)	
Experimental arm 1 (Aim 1a): Education about clinical trials and cancer research via provider portal education to cancer survivors, caregivers, and the public.
 
Experimental arm 2 (Aim 1b): Education about clinical trials and cancer research via online video and module.

Study Population	The main target population is adults aged 18 or older who reside in rural New Hampshire or Vermont; “rural” = Rural Urban Continuum Codes (RUCC) 7—9 counties (Coos and Sullivan County, NH; Caledonia, Windsor, Windham, Orange, Orleans, Lamoille, and Essex County, VT)

PROTOCOL TITLE: Education about Health and Cancer Study

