**3.3.** In order to implement education about clinical trials across 24 cancer centers, NCI/CRCHD has developed a set of key messages that all cancer centers must include in their educational activities, and the cancer centers are tailoring the educational messaging/curriculum and delivery of activities to be locally-relevant and tailored to the needs of our catchment area. NCI/CRCHD has also developed a pre-test and a post-test (surveys- see attached) that will be administered immediately preceding and proceeding our educational activities, with the intent of evaluating whether the educational interventions changed the participants' knowledge of, attitudes toward, and behavioral intentions regarding taking part in clinical trials and research. NCI/CRCHD has asked us to track whether participants in our interventions go on to enroll in trials/studies in the six-months following our intervention (via our PIs' and Office of Clinical Trials' research records).

PROTOCOL TITLE: Education about Health and Cancer Study

This study will help measure and evaluate the effectiveness of different models of educating people about clinical trials. The data will be aggregated at a national level to assess the overall NCI/CRCHD activity. The data will be analyzed at the local/regional level to inform DCC's Community Outreach and Engagement program's future outreach models. Given the limited literature regarding the effectiveness of education on clinical trials knowledge, attitudes, and enrollment, this study will contribute meaningful and important information.

References:

- 1 *Ford, J. G., Howerton, M. W., Lai, G. Y., Gary, T. L., Bolen, S., Gibbons, M. C., ... & Powe, N. R. (2008). Barriers to recruiting underrepresented populations to cancer clinical trials: a systematic review. Cancer: Interdisciplinary International Journal of the American Cancer Society, 112(2), 228-242.*
2. *Taylor, H., & Leitman, R. Misconceptions and lack of awareness greatly reduce recruitment for cancer clinical trials.[article online, Health Care News, Vol. 1, Issue 3]. Rochester (NY): Harris Interactive, Inc.; 2001 Jan 22 [cited 2001 Mar 29]. [3 p].*

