- x- E-mailing de-identified pre and post survey data to NCI/CRCHD and/or its contractor for data entry, quality control, and national aggregation. E-mailing of tracking excel spreadsheet to NCI/CRCHD and/or its contractor.
- y- Local analysis of data to determine effect of study objectives

If any individuals contact the research team indicating they had difficulties completing the surveys online, we will seek information from them to match their survey record (e.g., their initials, time of day/date they were completing the survey) and provide them with assistance by phone and/or email to enable them to complete the study procedures. In some cases, this may entail providing a separate survey link to them by

PROTOCOL TITLE: Education about Health and Cancer Study  
email for them to complete.

PROTOCOL TITLE: Education about Health and Cancer Study

We are discontinuing our control arm. Because the control arm was part of our local research procedures and not part of NCI's national initiative, we will not be providing any control arm data to NCI or its contractor.

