PROTOCOL TITLE: Education about Health and Cancer Study data (all de-identified, using unique identifier) from our experimental arms (not control arm). We will also provide NCI/CRCHD/its contractor with general information about the in-person outreach (e.g., dates, locations, number of attendees), about the social media ad reach/metrics, and, as needed, cost. [name], [name], [name], [name], [name], [name] and the research team will be responsible for sharing the data with NCI/CRCHD/its contractor. Please see the attached document from NCI/CRCHD entitled *Data Collection Storage and Security* for additional information.

PROTOCOL TITLE: Education about Health and Cancer Study

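### Without a control arm, Section 17.1 and Hypotheses 1 and 2 should claim change within each arm, not change caused by the education

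*Protocol*

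**What the plan says.** Section 17.1 is the protocol's only statement of the analysis. Its tests are to "determine whether participants experienced changes in knowledge, attitudes, behavioral intentions, and behavior as a results of any of the study arms", and it adds that "changes will be look at across groups" without naming the groups. Section 3.3 gives the pre-test and post-test the same purpose, "with the intent of evaluating whether the educational interventions changed the participants' knowledge of" clinical trials, along with attitudes and intentions. Section 2.1 lists evaluating effectiveness as a purpose. Both hypotheses in Section 2.2 predict that the education will succeed in raising knowledge and intent.

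Section 1.0 describes a cohort study with pre, post and follow-up measurements. Section 6.0, at the end of the Arm 2 procedures, states "We are discontinuing our control arm". On control data it says only that "we will not be providing any control arm data to NCI or its contractor"; Section 17.3 repeats that exclusion. Sections 19 and 24.1 still mention a control arm in passing. The current text gives neither a number of control participants nor a method of allocation.

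**The concern.** The wording in 17.1 attributes any observed change to the arm. A single group measured twice can show that scores moved, but not why. Followed as written, the plan would count any significant rise in knowledge or intent as support for Hypotheses 1 and 2, whatever its cause.

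This matters because the results have two declared uses: shaping the cancer center's future outreach models (Section 3.3) and academic dissemination (Section 8.0). An effectiveness claim made there would go beyond what the design can support.

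**Working it through.** **1. Sizes.** Section 12.0 sets completion targets of up to 50 (Arm 1) and 200 to 250 (Arm 2), and expects up to 900 consents with about one third completing. Check: 900 × 1/3 = 300, and 50 + 250 = 300, so the figures agree. The protocol states no alpha, effect size or standard deviation.

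**2. Is there another comparator for knowledge, attitudes and intentions?**
- Arm 1 against Arm 2: both receive education, they are recruited from different sources, and only Arm 2 is limited to rural counties (Section 10). The difference between them does not isolate the effect of education.
- Aggregate enrollment at the cancer center (Section 6.1, Arm 1, step h): this concerns enrollment only. Part (c) of each hypothesis is therefore outside this point.

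Neither fills the gap.

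**3. Which other explanations do the procedures leave open?**
- Repeat testing: everyone analysed answers a survey before and after. In Arm 2 both fall in one session (Section 22.1).
- Response bias in paid completers: gift cards are given in both arms (Section 13.5), and those who do not finish pre-test, education and post-test are withdrawn (Section 14.1). The change is thus measured in about one third of those who consent. The rest include people found ineligible as well as those who drop out.
- Order of questions: in Arm 2, pre-screening for open trials (step q) comes before the intention items (step r). In Arm 1, step f lists pre-screening before the attitude and intention items. A shift in intent may therefore reflect the pre-screening.

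**4. How easily would such a shift be declared significant?** Assume no education effect, a non-education shift of d standard deviations of the change score, and a paired test at two-sided 0.05. The probability of a significant improvement is approximately Φ(d√n − 1.96). For d = 0.2:
- n = 200: 0.2 × 14.142 − 1.96 = 0.868, giving 0.807
- n = 250: 0.2 × 15.811 − 1.96 = 1.202, giving 0.885

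| n | d = 0 | d = 0.1 | d = 0.2 | d = 0.3 |
|---|---|---|---|---|
| 50 | 0.025 | 0.105 | 0.293 | 0.564 |
| 200 | 0.025 | 0.293 | 0.807 | 0.989 |
| 250 | 0.025 | 0.352 | 0.885 | 0.997 |

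The paired t-test gives nearly the same: 0.284, 0.804 and 0.883 at d = 0.2 for n = 50, 200 and 250. The shift and the alpha are assumptions; the documents supply neither.

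**5. What could control records add, if any exist?** Suppose m controls completed and the same number of Arm 2 participants came from the same period (both assumed). The 95% half-width for the difference in mean change is 1.96√(2/m) SD: 0.51, 0.39 and 0.28 for m = 30, 50 and 100. Using all 250 Arm 2 participants, 1.96√(1/m + 1/250) gives 0.38, 0.30 and 0.23, but that would mix recruitment periods.

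**The case against.** The design is disclosed. Section 1.0 calls it a pre/post cohort, Section 3.3 attributes the surveys to the national program, and nothing presents the arms as controlled. Same-session testing in Arm 2 leaves little room for outside events to change scores. The survey items are not shown, so it is not known that the pre-test and post-test questions are identical. Response bias produces a change only if it differs between the two occasions. The assumed shift has no source in the documents.

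All of this stands, and it limits how confidently any one rival explanation can be asserted. It does not rescue the causal phrase. Disclosing an uncontrolled design does not license attribution, and the order of pre-screening and intention items is written into the procedures.

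Two stronger readings are tempting, and the documents support neither.
- A reader might infer that control data are held and have been shut out of the analysis. The text bars only their transfer to the national program and does not forbid local use. It does not confirm that any control participant completed, and a statistical analysis plan could assign such data a role.
- A reader might infer from the table that the test's error rate is inflated above 5%. It is not. A non-zero shift is a real change, and the paired test detects it correctly.

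**Conclusion.** The point holds as a mismatch between claim and design. For knowledge, attitudes and intentions, Section 17.1 and Hypotheses 1 and 2 attribute to the education what two uncontrolled pre/post groups cannot attribute. At the planned Arm 2 size, an assumed non-education shift of 0.2 SD would be significant about 80% to 88% of the time with no education effect. With 50 in Arm 1 the figure is about 28%. These figures illustrate the risk; they do not estimate the shift in this study. Nothing here shows that the education is ineffective, or that the pre/post analysis should be dropped. The correction is to the wording, but it changes what the study may conclude.

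**What to change.** - In Section 17.1, replace the attribution of change to the study arms with: *from pre-test to post-test within each arm*.
- Add a sentence that within-arm change alone is not evidence that the education was effective.
- Reword the knowledge and intent parts of Hypotheses 1 and 2 to match, for example: *scores will be higher at post-test than at pre-test within the arm*.

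Optional and secondary: if control participants completed before that arm closed, report the Arm 2 minus control difference in post-score, adjusted for pre-score, using Arm 2 participants from the same period. Treat it as supportive only, unless allocation was randomized, and compute its interval from the actual same-period numbers. It says nothing about Arm 1.

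Cost: edits to two sections and, at most, one extra local analysis, with no new participants or procedures. The downside is a more modest claim, and a wide interval if few controls completed.

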**Data quality control:**

Experimental Arm 1 (Aim 1a):

The DCC research team will review results from Qualtrics survey. . If the review reveals a potential data quality issue, the research team will determine how widespread the issue is and will inform NCI/CRCHD (or its independent contractor) for guidance. At the end of the project, NCI/CRCHD plans to have its independent contractor review all data collected for quality.

Experimental Arm 2 (Aim 1b):

The DCC research team will review data collected from advertisement wave that is launched to check for possible problems such as errors in computer display to participants, errors in skip logic, and robotic responses. If the audit reveals a potential data quality issue, the research team will review additional data to determine how widespread the issue is and will work with the appropriate DHH and DCC colleagues (e.g. tech support) and NCI/CRCHD to address the issues, as needed. To aid in identifying bot and fake responses and support data integrity, we will use several features in Qualtrics, including the bot detector and turning 'location' settings to 'on' to track location of respondents (e.g., IP address).

As with any study that collects information about health, it is important to secure this information. As stated below, multiple safeguards have been put in place to minimize the risk of possible data disclosures. We do not plan to obtain a certificate of confidentiality.

17.3. Original paper research forms/data will be kept in a locked filing cabinet at DHMC for six years. All electronic files will be stored on password-protected, encrypted computers that are property of the Dartmouth Cancer Center. Electronic data will also be stored in password-protected sites/applications supported by Dartmouth College/DHH, such as Qualtrics and /Sharepoint/One Drive; access will only be granted to official study team members. All files, paper and electronic, at DHH will be destroyed after six years.

De-identified survey copies/survey data will be emailed/mailed to NCI/CRCHD/its contractor for data processing on a quarterly basis. Data collected from participants to be shared include pre-test, post-test, and follow-up

PROTOCOL TITLE: Education about Health and Cancer Study data (all de-identified, using unique identifier) from our experimental arms (not control arm). We will also provide NCI/CRCHD/its contractor with general information about the in-person outreach (e.g., dates, locations, number of attendees), about the social media ad reach/metrics, and, as needed, cost. [name], [name], [name], [name], [name], [name] and the research team will be responsible for sharing the data with NCI/CRCHD/its contractor. Please see the attached document from NCI/CRCHD entitled *Data Collection Storage and Security* for additional information.

PROTOCOL TITLE: Education about Health and Cancer Study

**18.0 Provisions to Monitor the Data to Ensure the Safety of Subjects\***

N/A- This study involves only minimal risks. The primary risk is related to privacy/confidentiality, however, we are addressing that risk on the Information sheet by stating that we are putting in place the following processes for participant protection:

- Study team members are trained on all procedures
- Study computers are encrypted and have passcodes, study data collection will have passcode access only, and the physical location of the research material is locked
- All study participants will have a unique identifier code assigned to them stored separately from identifiable study information that will be collected for follow-up and gift card distribution

**19.0 Provisions to Protect the Privacy Interests of Subjects**

19.1 and 19.2

Experimental Arm 1 (Aim 1a): Participants will complete the information sheet and study surveys online.

The information sheet provides information about how participants' contact/identifying information will be used. Those who pre-screen as being potentially eligible for an open study/trial will provide permission for their contact/identifying information to be shared with the study teams and/or the clinical team (e.g., Research Nurses/Nurse Navigators) (see enclosed pre-screening question sheet with permission question and information sheet).

Experimental Arm 2 and Control Arm (Aim 1b):

Contact/identifying information requested from participants will be managed and stored separately from the study data.

The information sheet provides information about how participants' contact/identifying information will be used. Those who pre-screen as being potentially eligible for an open study/trial will provide permission for their contact/identifying information to be shared with the study teams and/or the clinical teams (e.g., Research Nurses/ Nurse Navigators) (see enclosed information sheet and see Qualtrics PDF).

19.3 Any study forms containing identifiable information will not be available to all study members, with an exception of the Qualtrics account/survey, which will be managed by most study team members. Only the study coordinators and a manager/sub-investigator will have access to any other identifying information, and this information will only be accessed for purposes of gift card distribution and follow-up data tracking.

PROTOCOL TITLE: Education about Health and Cancer Study

## **20.0 Compensation for Research-Related Injury**

N/A- This study involves no more than minimal risk to subjects.

## **21.0 Economic Burden to Subjects**

**21.1** Study participants will not be subject to any costs for participating in the study/educational interventions.

Should our intervention be effective in encouraging them to participate in a clinical trial or research study, all costs associated with those trials/studies are beyond the scope of this study.

## **22.0 Consent Process**

### **22.1. Experimental Arm 1 (Aim 1a):**

23 Once the prospective participant clicks the link in the email invitation to learn more about the study, they will be presented with an information sheet with HIPAA authorization (attached) and asked to read it before proceeding. As part of the information sheet, participants will be provided with contact information for the study team should they have any questions before proceeding. They will e-sign the form with initials before continuing forward (see enclosed PDF of Qualtrics survey for consent, as well as information sheet file). They will then be presented with eligibility questions. If they are eligible for the study, they will be asked to move forward to complete the remaining study procedures.

